### 9.2. Other Efficacy Analyses

Other efficacy analyses will be performed on FAS and PPS. C-peptide, insulin, HOMA- $\beta$ , HOMA-IR, HOMA2- $\beta$ , HOMA2-IR, I0/G,  $\Delta$ I30/ $\Delta$ G30,  $\Delta$ C30/ $\Delta$ G30,  $\Delta$ I120/ $\Delta$ G120 and DI will be included in Other efficacy endpoints. Change from baseline in those endpoints will be summarized for each of treatment groups. Composite HbA1c response rate (the proportion of subjects with HbA1c < 7.0%, no hypoglycemia and no weight gain) and time to hyperglycemia withdraw will be provided.

Change from baseline in C-Peptide (including fasting C-Peptide, 0.5-hour postprandial C-Peptide and 2-hour postprandial C-Peptide) and change from baseline in insulin (including fasting insulin, 0.5-hour postprandial insulin, 2-hour postprandial insulin) will be provided. MMRM will be used, where the model is the same as primary endpoint analysis model.

HOMA- $\beta$ , HOMA-IR, HOMA2- $\beta$ , HOMA2-IR, I0/G0,  $\Delta$ I30/ $\Delta$ G30,  $\Delta$ C30/ $\Delta$ G30,  $\Delta$ I120/ $\Delta$ G120 and change from baseline in DI will be analyzed and compared using ANCOVA for each treatment group. The model includes the factors of treatment group, pooled site, interaction of pooled site with treatment group and baseline value of corresponding endpoint. If the interaction is not significant (2-sided alpha 0.1), then remove the interaction of pooled site with treatment group from model.

### **9.2.1. Fasting C-Peptide**

MMRM will be used, where the model is the same as primary endpoint analysis model. The model includes the factors of treatment group, visit, interaction of visit with treatment group, pooled site and baseline fasting C-Peptide. The point estimate and 95% CI of mean difference between treatment groups (HMS5552 75mg BID vs. Placebo BID) will be calculated.

### **9.2.2. 0.5-Hour Postprandial C-Peptide**

MMRM will be used, where the model is the same as primary endpoint analysis model. The model includes the factors of treatment group, visit, interaction of visit with treatment group, pooled site and baseline 0.5-hour postprandial C-Peptide. The point estimate and 95% CI of mean difference between treatment groups (HMS5552 75mg BID vs. Placebo BID) will be calculated.

### **9.2.3. 2-Hour Postprandial C-Peptide**

MMRM will be used, where the model is the same as primary endpoint analysis model. The model includes the factors of treatment group, visit, interaction of visit with treatment group, pooled site and baseline 2-hour postprandial C-Peptide. The point estimate and 95% CI of mean difference between treatment groups (HMS5552 75mg BID vs. Placebo BID) will be calculated.

### **9.2.4. Fasting Insulin**

MMRM will be used, where the model is the same as primary endpoint analysis model. The model includes the factors of treatment group, visit, interaction of visit with treatment group, pooled site and baseline fasting insulin. The point estimate and 95% CI of mean difference between treatment groups (HMS5552 75mg BID vs. Placebo BID) will be calculated.

### **9.2.5. 0.5-Hour Postprandial insulin**

MMRM will be used, where the model is the same as primary endpoint analysis model. The model includes the factors of treatment group, visit, interaction of visit with treatment group, pooled site and baseline 0.5-hour postprandial insulin. The point estimate and 95% CI of mean difference between treatment groups (HMS5552 75mg BID vs. Placebo BID) will be calculated.

### **9.2.6. 2-hour postprandial insulin**

MMRM will be used, where the model is the same as primary endpoint analysis model. The model includes the factors of treatment group, visit, interaction of visit with treatment group, pooled site and baseline 2-hour postprandial insulin. The point estimate and 95% CI of mean difference between treatment groups (HMS5552 75mg BID vs. Placebo BID) will be calculated.

### **9.2.7. Composite HbA1c Response Rate.**

The composite HbA1c response rate is defined as HbA1c < 7.0%, no hypoglycemia and no weight gain during double-blind treatment period. Hypoglycemia events is defined by each of two following principles: 1) serious hypoglycemia or fingertip/venous plasma glucose  $\leq 3.9$  mmol/L; 2) serious hypoglycemia or fingertip/venous plasma glucose  $\leq 3.0$  mmol/L. No weight gain is defined as increase of weight  $\leq 0.5$ kg.

HbA1c Response Rate and composite HbA1c response rate will be calculated on basis of data imputed using LOCF method. Odds ratio (OR) and its 95% CI between two treatment groups will be estimated using logistic regression method. The model includes the factors of treatment group, pooled site, interaction of pooled site with treatment group and baseline HbA1c. If the interaction is not significant (2-sided alpha 0.1), then remove the interaction of pooled site with treatment group from model.

### **9.2.8. Time to Hyperglycemia Withdraw**

Time to hyperglycemia withdraw is defined as time from the first exposure of study treatment to the withdrawal time caused by hyperglycemia events or censor. Kaplan-Meier Plot will be displayed, and log-rank test will be performed to compare the median time difference between groups. Subjects with no events will be censored.

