**4.5.2 Withdrawal due to Hyperglycemia**

Between Visits 2 and 15, subjects should carry out SMBG according to SMBG guidance (refer to Appendix 4 for procedures of SMBG). Subjects should contact the Investigator timely if plasma glucose exceed the value specified in SMBG guidance. Depending on the fingertip plasma glucose values, diet and exercise condition, the Investigator determines whether the subjects should return to study sites in advance for laboratory tests.

If a subject has a FPG value reaching the following criteria twice (at least once tested in the central laboratory) without any apparent causes at two consecutive visits, the Investigator will evaluate whether the subject will withdraw from the study with the reason recorded as hyperglycemia based on subject's actual situation.

1. Day 1–before Week 12: venous FPG (central laboratory)  $\geq 13.3$  mmol/L
2. Week 12–before Week 24: venous FPG (central laboratory)  $\geq 11.1$  mmol/L
3. Week 24–Week 52: venous FPG (central laboratory)  $\geq 11.1$  mmol/L.

If a subject is confirmed to withdraw from the study due to hyperglycemia, the subject must complete termination visit before withdrawal (refer to Section 4.6). Then, the study medications can be discontinued and routine diagnosis and treatment can be started.

The Investigator must ensure no other causes can be identified to explain poor glycemic control except for lack of efficacy (e.g., acute inflammations/infections, concomitant treatments, etc.). If the disease aggravation is unexpected progression, it should be reported as an AE.

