## 7.8 Laboratory Safety Assessments

Blood and urine samples are collected for laboratory assessments. The collecting date and time are recorded on the laboratory tests application form. The samples are processed in the central laboratory and the results are reported to study sites within 72 hours.

All subjects are suggested to go to each visit in fasting state between 7:00 am and 10:00 am. The subjects should be informed to avoid heavy physical activities and intake of high fat and high calorie food one day before the visit. Food and beverage except for water are prohibited within 8 hours before the visit. Also, the subjects are informed of not taking the study medications by themselves in the morning of the visit day. Other permitted medications can only be administered with water.

All samples are collected by authorized study staffs, and processed per manuals in the central laboratory. The latest laboratory reference range is provided to study sites during the study. The laboratory results are compared with the reference range values. Results exceeding the normal range are marked. The Investigator evaluates the abnormal results and decides whether they are clinically significant or not.

See Section 7.1.3 for how to record and report AEs relevant to laboratory tests.

The following laboratory safety parameters are measured:

- Hematology: hemoglobin, hematocrit, erythrocytes count, leukocytes count, neutrophils, basophils, eosinophils, monocytes, lymphocytes, and platelet count
- Urinalysis: pH, specific gravity, protein, glucose, erythrocytes, leukocytes, and ketone bodies
- Blood biochemistry: glucose, total bilirubin, ALT, AST, gamma-glutamyl transferase, alkaline phosphatase, albumin, total protein, lactate dehydrogenase, urea nitrogen, creatinine, uric acid, sodium, potassium, chloride, calcium, creatine kinase, creatine kinase isoenzyme, total cholesterol, high-density lipoprotein cholesterol, low-density lipoprotein cholesterol, and triglyceride.

All methods, instruments, and quality control requirements for laboratory tests are described in detail in the manual of central laboratory.

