## 2. Summary of Key Protocol Information

### 2.1. Changes to the Protocol Defined Statistical Analysis Plan

Protocol	SAP	Reasons
Alternative hypothesis: After 24-week treatment of HMS5552 75 mg BID, the decrease of HbA1c level in subjects with T2DM is significantly different with placebo group	Alternative hypothesis: After 24-week treatment of HMS5552 75 mg BID, the decrease of HbA1c level in subjects with T2DM is different with placebo group	“significantly” was removed, which makes SAP more accurate while no conflict with protocol.
No other efficacy endpoints in protocol.	2.2.2.3. Other Efficacy Endpoints 
 
Change of fasting insulin from baseline
 
Change of 0.5-hour postprandial insulin from baseline
 
Change of 2-hour postprandial insulin from baseline
 
Change of fasting C-Peptide from baseline
 
Change of 0.5-hour postprandial C-Peptide from baseline
 
Change of 2-hour
 
	Exploration analyses

postprandial C-Peptide  
from baseline  
• Change of HOMA- $\beta$   
from baseline  
• Change of HOMA-  
IR from baseline  
• Change of HOMA2-  
 $\beta$  from baseline  
• Change of HOMA2-  
IR from baseline  
• Change of I0/G0  
from baseline  
• Change of  
 $\Delta I30/\Delta G30$  from baseline  
• Change of  
 $\Delta C30/\Delta G30$  from baseline  
• Change of  
 $\Delta I120/\Delta G120$  from  
baseline  
• Change of  
Disposition Index (DI)  
from baseline  
• Time to  
hyperglycemia Withdraw  
• Composite HbA1c  
response rate (the  
proportion of subjects with  
HbA1c < 7.0% and without  
incidence of  
hypoglycemic events and  
no weight gain)

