## 5.2. Stratification Factors

IWRS system will be used to assign the randomization codes to unique subjects who meet randomization criteria based on stratification factors (baseline HbA1c level  $\leq 8.5\%$  or  $> 8.5\%$ ) and the block size.

Unless otherwise specified, sites will be included in models for the study analysis. Baseline of other parameters will be also included in the specified analysis.

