#### 9.1.4 Change from Baseline in Fasting Plasma Glucose (FPG)

MMRM will be used, where the model is the same as primary endpoint analysis model. The model includes the factors of treatment group, visit, interaction of visit with treatment group, pooled site and baseline fasting plasma glucose. The point estimate and 95% CI of mean difference between treatment groups (HMS5552 75mg BID vs. Placebo BID) will be calculated.

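### The log-rank test for time to hyperglycaemia withdrawal is described as comparing medians, and it and several other models leave out the HbA1c stratum used to randomise (minor)

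*Supplement*

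**What the plan says.** SAP 9.2.8 defines the endpoint as "time from the first exposure of study treatment to the withdrawal time caused by hyperglycemia events or censor" and adds "Subjects with no events will be censored". It plans a Kaplan-Meier plot and says that a "log-rank test will be performed to compare the median time difference between groups". It names no stratification, hazard ratio, event proportion or end of follow-up. The change table in SAP 2.1 ("No other efficacy endpoints in protocol") shows that the endpoint was added in the SAP as exploratory.

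The event depends on judgement. Under protocol 4.5.2, after two qualifying FPG values, "the Investigator will evaluate whether the subject will withdraw from the study with the reason recorded as hyperglycemia".

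Protocol 3.3.5 and SAP 5.2 stratify randomisation by HbA1c, 8.5% or below against above. On modelling, SAP 5.2 then says only: "Unless otherwise specified, sites will be included in models for the study analysis". The FPG model in SAP 9.1.4 is called the same as the primary model, but its factor list ends with "pooled site and baseline fasting plasma glucose" where the primary model has baseline HbA1c. SAP 9.1.5 (PPG) and 9.2.1 to 9.2.6 (C-peptide, insulin) make the same kind of swap. The weight ANCOVA in SAP 9.3.5 has site and its own baseline only. Baseline HbA1c is kept in the primary MMRM (8.1), the LOCF ANCOVA (8.1.1) and the responder models (9.1.2, 9.1.3, 9.2.7).

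**The concern.** Two separate matters meet in SAP 9.2.8.

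First, the sentence gives the test a hypothesis that it does not test. A log-rank test asks whether the two withdrawal-time distributions differ. The only contrast named is a difference in medians, and that exists only if both Kaplan-Meier curves fall to 50%. If they do not, the analysis gives a p-value with no measure of size. The open end of follow-up adds to this: placebo subjects switch to HMS5552 after Week 24, so a test run to Week 52 would mix two treatments in one arm.

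Second, a factor that was balanced by design is left out of the analysis. If the stratum predicts outcome, the analysis claims more variability than the design leaves, so tests are conservative and intervals slightly wide.

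**Working it through.** **The plan's own figure.** Inputs from SAP 2.4: 300 and 150 subjects, difference 0.4, SD 1.2, two-sided 0.05.
- SE = 1.2 × √(1/300 + 1/150) = 1.2 × 0.1 = 0.12, and 0.4/0.12 = 3.33.
- Normal power = Φ(3.33 − 1.96) = 91.5%. Noncentral t with 448 df gives 91.41%. The stated 91.4% is reproduced.
- 450/(1 − 0.20) = 562.5, so 563, rounded up to a multiple of 3 = 564 (376 + 188). The drop-out allowance is 564 − 450 = 114, for all causes.

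**Can a median difference be estimated at that drop-out?** Both curves must reach 50%. With no earlier censoring that takes 376/2 + 188/2 = 188 + 94 = 282 events, against 114 drop-outs of any kind.
- HMS5552: if all 114 were hyperglycaemia withdrawals in this arm, the curve would stand at 1 − 114/376 = 70%. If c of the 114 were instead censored before the events, the fall would be (114 − c)/(376 − c), which is smaller. The median is out of reach.
- Placebo: all 114 in this arm would be 114/188 = 61%, so its median is not excluded. It would need at least 94 of the 114 drop-outs to be on placebo. With other drop-outs censored first, the fewest hyperglycaemia withdrawals that suffice is 74, since (188 − 40)/2 = 74 and 74 + 40 = 114.
- The documents give no hyperglycaemia-withdrawal rate, so a range was simulated (450 subjects, 24 weeks, 10% other drop-out). At 10% to 30% placebo incidence neither median was reached in any run checked. At 55% (treatment HR 0.5) the placebo median was reached in 89% of runs and the HMS5552 median in none. At 70% the figures were 100% and 49%.

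**Cost of the unstratified log-rank test.** Assumptions: 450 subjects, 2:1 blocks within stratum, 40% above 8.5%, treatment HR 0.5, 10% other drop-out over 24 weeks.

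| Placebo incidence | Stratum HR | Power, unstratified | Power, stratified |
|---|---|---|---|
| 10% | 3 | 45.7% | 46.5% |
| 10% | 6 | 45.1% | 47.2% |
| 20% | 3 | 74.9% | 75.8% |
| 20% | 6 | 71.7% | 75.6% |
| 30% | 3 | 88.6% | 90.1% |
| 30% | 6 | 86.2% | 90.4% |

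Type I error (treatment HR 1) was 2.8% to 5.0% unstratified and 4.7% to 5.7% stratified.

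**Cost in an FPG-type model.** A single-visit ANCOVA stood in for the MMRM: 450 subjects, correlation of baseline FPG with HbA1c 0.4 or 0.7, HbA1c effect 0.2 or 0.5 residual SD per SD, treatment effect 0.3 SD, 3,000 runs each. Without the stratum the SE was 0.4% to 5.5% larger and power 0.3 points lower (84.6% against 84.9%) to 3.7 points lower (78.0% against 81.7%). Type I error was 3.9% to 5.2%; the simulation error is √(0.05 × 0.95/3000) = 0.4 points, so 5.2% is not a real excess.

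**The case against.** The best defence is that little depends on this. The endpoint is exploratory, SAP 5.3 rests the confirmatory claim on one primary endpoint, and the Kaplan-Meier plot and log-rank p-value stay computable and valid whatever the sentence calls them. All of that stands, and it sets the weight.

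The cut-off is also partly covered: SAP 5.3 makes Week 52 efficacy descriptive. But SAP 5.4 promises hypothesis-test results for the double-blind and the whole-treatment analyses alike, and 9.2.8 does not say which applies.

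Four stronger readings are tempting, and the documents do not support them.
- That no median can exist. The 20% is a planning allowance, not a cap; no event rate is given; withdrawal is the investigator's decision. The placebo median is unlikely, not impossible.
- That leaving out the stratum costs much power. With a stratum hazard ratio of 8, 38% placebo incidence, 45% in the high stratum and treatment HR 0.55, 600 simulated trials gave 91.0% stratified against 85.7% unstratified. Those inputs imply about 25.2% incidence on HMS5552, hence (2 × 25.2% + 38%)/3 = 29.5% of all subjects withdrawing for hyperglycaemia, above the whole allowance. No stratum effect is documented.
- That the omission risks false positives. The simulations point the other way.
- That subjects near 8.5% will be put in the wrong stratum. Baseline HbA1c is drawn at Visit 4 and "the results are reported to study sites within 72 hours", so the value entered in IWRS was probably the Visit 3 one. That is an inference, and no SAP model rebuilds the stratum from baseline. It only bears on which variable the fix should name.

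**Conclusion.** The wording in SAP 9.2.8 is wrong about what a log-rank test compares, and the median difference that it names is not expected to be estimable at the planned drop-out. The section also lacks an effect estimate and a stated cut-off. This part rests on the plan's own numbers plus the assumption that actual drop-out is near 20%.

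The missing HbA1c stratum is a small loss of efficiency, not a validity problem: about 1 to 4 power points for the log-rank test. The upper end depends on assumption. At 30% placebo incidence and stratum HR 6 the simulated trials averaged 92.4 events, 92.4/450 = 20.5% of subjects, which alone fills the allowance. At 10% incidence the loss was 0.8 to 2.1 points.

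Severity is minor. The primary analysis already adjusts for baseline HbA1c and is unaffected.

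**What to change.** In SAP 9.2.8:
- delete the reference to medians and state that the log-rank test compares the withdrawal-time distributions over the double-blind period, censoring at its end;
- stratify the test by the HbA1c stratum recorded in IWRS at randomisation, not by a category rebuilt from the baseline value;
- report a hazard ratio from a Cox model with the same stratification, and the Week 24 Kaplan-Meier proportion withdrawn for hyperglycaemia in each arm, all with 95% CI.

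In SAP 9.1.4, 9.1.5, 9.2.1 to 9.2.6 and 9.3.5, add the IWRS HbA1c stratum as a fixed effect.

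The cost is a few sentences of SAP text and one class variable that IWRS already stores. It needs no new data and no change to the sample size.

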## **9.3. Safety Analyses**

Safety Analyses will be performed on Safety set.

### **9.3.1. Exposure of Subjects**

Duration of exposure(days), actual dose and compliance of subjects will be summarized for double-blind period and open-label period respectively.

### 9.3.2. Adverse Events

Adverse events will be coded using MedDRA version 22.0.

Adverse events start before the first exposure to study treatment in double-blind treatment period will be included in the listing of all adverse events.

Treatment emergent adverse events (TEAEs) will be summarized for double-blind period and open-label period respectively. TEAEs are defined as any adverse event present after the first exposure to study treatment or any already presented events that worsened after the first exposure to study treatment.

TEAEs in double-blind treatment period: any adverse event present after the first exposure to study treatment or any already presented events before first double-blind dose administration that worsened after the first exposure to study treatment till the end of double-blind treatment period.

Treatment related adverse events: Adverse events that “Related” or “Probably related” to study treatments.

Important Adverse events: any adverse events, except serious adverse events, leads to results in actions of medical treatment (such as dose discontinuation, dose reducing or symptomatic approach treatment) and abnormal hematological or other lab test results.

Incidence rate of adverse events, treatment related adverse events, serious adverse events and adverse events result in withdrawal from study will be summarized and counted by SOC/PT for each treatment group. The frequency of AEs will be counted for each subject only once per PT name. The difference incidence rate between treatment groups will be compared using Fisher’s Exact test.

Adverse Events will be summarized by severities, if an adverse event occurs more than once on a given subject, then the worst will be counted.

Adverse events with incidence rate  $\geq 2\%$  and  $\geq 5\%$  will be summarized by PT name.

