### 7.2.5 Causality Assessment

The Investigator should assess the causal relationship between the AE and the study medications through medical and scientific judgement. The following criteria can be referred to:

1. **Related:** The AE occurrence follows a reasonable temporal relationship with administration of the study medication. The AE is consistent with the known profile of the study medication. The event is improved when the dose of study medication is decreased or stopped. The event reoccurs when the study treatment is restarted. The AE can't be explained by subjects' medical condition or alternative treatment.
2. **Possibly related:** The AE occurrence follows a reasonable temporal relationship with

administration of the study medication. The AE is consistent with the known profile of the study medication. The AE alleviates or becomes not obvious after reducing the dosage or stopping the study medication. The subjects' medical condition or alternative treatment may lead to the event.

3. **Unlikely related:** The temporal relationship between the AE occurrence and administration of the study medication is not clear. The AE may not be consistent with the known profile of the study medication. The subjects' medical condition or alternative treatments may lead to the event.
4. **Not related:** There is no reasonable temporal relationship between the AE occurrence and administration of the study medication. The AE is not consistent with the known profile of the study medication. The subjects' medical condition or alternative treatments may lead to the event. The AE improves or disappears when the disease condition improves or alternative treatment is stopped.

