## 7.6 Post-study AE Reporting

At any time after the study ends, if the Investigator is informed of any AE which is considered possibly related to the study medication, the Investigator needs to promptly report the event to the Clinical Drug Safety department of the Sponsor. The follow-up information of the SAEs after database lock also needs to be reported to the Clinical Drug Safety department of the Sponsor. The contact information is: Email: [[contact]](mailto:[contact]), [contact], [contact].

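### SAP 9.3.2 defines treatment-related adverse events with a causality level that the protocol scale does not contain, and does not name the level *Possibly related*

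*Supplement*

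**What the plan says.** Protocol v1.1, section 7.2.5 Causality Assessment (the number 7.2.5 is also used for AE Outcome), describes four levels for the investigator's judgement:

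1. "Related: The AE occurrence follows a reasonable temporal relationship with administration of the study medication"
2. "Possibly related: The AE occurrence follows a reasonable temporal relationship with" administration of the drug
3. "Unlikely related: The temporal relationship between the AE occurrence and administration of the study medication is not clear"
4. "Not related: There is no reasonable temporal relationship between the AE occurrence and administration of the study medication"

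SAP section 9.3.2 then sets the rule for the analysis: "Treatment related adverse events: Adverse events that “Related” or “Probably related” to study treatments". It uses that rule in the incidence tables: "Incidence rate of adverse events, treatment related adverse events, serious adverse events and adverse events result in withdrawal from study will be summarized" by SOC and PT for each treatment group, with incidence compared between groups by Fisher's exact test.

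SAP section 9.3.3 has a separate breakdown of hypoglycemia by relationship to treatment, with two values only, Related and Not Related. It does not say how these two values are derived.

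**The concern.** A derived safety variable has to be built from values that are actually recorded. The SAP selects on one value that is on the protocol scale and one that is not, and it passes over the protocol's second positive level. A programmer who follows the text literally will select *Related* alone and get no match on the second term.

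The level at risk matters. Under the protocol criteria a *Possibly related* event is plausible in time, fits the known profile of the drug and eases when the dose is reduced or stopped. Protocol section 7.6 takes the same level as its threshold for reporting after the study: "any AE which is considered possibly related to the study medication". That section does not govern the analysis, but it shows that the protocol treats the level as a positive attribution.

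At stake are the treatment-related incidence in each arm and its between-arm test. SAP section 3.1 says that the results of the first analysis go to the regulator in support of registration.

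**Working it through.** No sample size, power or rate enters this point, so there is no stated figure to reproduce. The check compares labels and then asks in which direction a mismatch would act.

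**Step 1. Labels side by side.**

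| Protocol v1.1, 7.2.5 | Named as treatment-related in SAP 9.3.2? |
|---|---|
| Related | Yes |
| Possibly related | No |
| Unlikely related | No |
| Not related | No |
| (no such level) | *Probably related* |

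The two sets share one label, *Related*.

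**Step 2. What separates the two positive levels.** The protocol's criteria overlap on three points: plausible timing, consistency with the known profile, and improvement on reduction or withdrawal of the drug. *Related* adds recurrence on restart and the absence of another explanation. *Possibly related* allows that the subject's condition or another treatment may be the cause. The protocol offers these as criteria for reference, not as strict requirements. Even so, *Related* alone is clearly the narrower class.

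**Step 3. Is there a bridge elsewhere in the SAP?** The table of changes from the protocol (SAP 2.1) lists no change of causality scale. Section 9.3.2 contains no mapping between the two sets of terms. SAP section 1 cites a case report form (v1.1) and section 4 refers to an attached table shell. Neither is shown, so the values collected and the table footnotes cannot be checked.

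**Step 4. Direction.** In one arm, let N be the number of subjects in the safety set, R the set of subjects with at least one *Related* event, and P the set with at least one *Possibly related* event.

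- Literal rule: incidence = |R| / N
- Rule in protocol terms: incidence = |R ∪ P| / N
- Shortfall: |P \ R| / N ≥ 0

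The literal rule therefore understates the treatment-related incidence, or at best leaves it unchanged. The same holds within each PT.

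**Step 5. Size.** The shortfall depends on how many subjects have a *Possibly related* event and no *Related* one. The documents give no counts by causality. An assumed share of events would not settle it either: SAP 9.3.2 counts a subject once per PT, so a share of events does not convert directly into a fall in the percentage of subjects.

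**Step 6. What is untouched.** Tables of all adverse events, serious events, events leading to withdrawal and events by severity do not use this definition. Nor does the primary efficacy analysis.

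**The case against.** The strongest reply is that this is translation, not a change of scale. The SAP re-renders protocol terms elsewhere. The hypoglycemia class that protocol section 4.5.1.1 calls *possible* symptomatic becomes *probably* symptomatic in SAP 9.3.3, which is the same swap. In the same place *relative* hypoglycemia becomes *comparative*, and *severe* becomes *serious*. The protocol has exactly two positive causality levels and the SAP names exactly two, so a one-to-one reading is natural. The silence of the table of changes also suggests that no new scale was intended.

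Most of this stands. A reader might infer from the mismatch that every *Possibly related* event will in fact be dropped. The documents do not support that: it follows on the literal reading only, and the form and shells that could decide between the readings are not shown.

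A reader might also infer that the comparison between arms would be distorted. That is not shown either. The same filter applies to both arms, causality in the double-blind period is judged under blinding, and there are no counts from which to derive an effect on the difference.

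The reply does not make the definition adequate. An intention inferred from a pattern of wording is not a pre-specified rule. As the text stands, either "Possibly related" events are excluded, or someone has to supply a mapping that the plan does not contain.

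**Conclusion.** Wrong as written; moderate severity. SAP 9.3.2 relies on a causality level that is absent from the protocol scale and does not name the protocol's second positive level. Taken literally, it removes *Possibly related* events from the treatment-related tables and their Fisher tests and so understates treatment-related events. Taken as a translation, it loses nothing. The documents available do not settle which reading will be programmed, and the size of any effect cannot be computed from them.

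The conclusion assumes that causality is collected on the protocol's four levels. If the case report form offers a *Probably related* option, the inconsistency lies between the form and the protocol, and the SAP should say which governs.

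The grade is moderate because the problem is confined to the treatment-related outputs and the other safety tables give a complete count of events.

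**What to change.** Before the first database lock and unblinding, restate the definition in SAP 9.3.2 in the protocol's own terms: treatment-related means *Related* or *Possibly related*. Check the terms against the case report form and carry the same wording into the table-shell footnotes.

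For the Related / Not Related split of hypoglycemia in SAP 9.3.3, first establish how causality is recorded. Protocol section 7.4 places it on a separate hypoglycemia page, whose options are not shown. If that page uses the same four levels, apply the same grouping and say so. If it is already two-valued, no mapping is needed.

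The cost is one SAP sentence, possibly a second for 9.3.3, and the footnotes. No data collection or other analysis changes.
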